4.3.8. Safety and Tolerability

The safety analysis set will be used for all safety and tolerability tables, figures and listings except where expressly noted.

4.3.8.1. Adverse Events and Serious Adverse Events

All AEs, both in terms of MedDRA PT and CTCAE grade, will be summarised descriptively by count (n) and percentage (%) for each treatment arm. The latest MedDRA dictionary version will be used for coding. Missing coding terms should be listed and summarised as "Not coded".

The summary tables will include all AEs that occurred after the start of treatment up until the end of the 28-day follow-up period. For the IDMCs, the 28-day follow-up period will be defined as 28 days following discontinuation of study treatment. For the primary analysis and any subsequent analysis, the 28-day follow-up period will be defined as 28 days following discontinuation of study treatment and before starting subsequent cancer therapy. Any events in this period that occur after a patient has received further therapy for cancer (following discontinuation of study treatment) will be flagged in the data listings for all analyses.

All reported AEs will be listed along with the date of onset, date of resolution (if AE is resolved), investigator's assessment of CTCAE grade and relationship to study treatment. Frequencies and percentages of patients reporting each PT will be presented (i.e. multiple events per patient will not be accounted for apart from on the episode level summaries).

Summary information (the number and percent of patients by treatment) by SOC and PT will be tabulated for:

- All AEs
- All AEs causally related to study treatment
- AEs with CTCAE grade 3 or higher
- AEs with CTCAE grade 3 or higher, causally related to treatment
- AEs with outcome of death
- AEs with outcome of death causally related to treatment
- AEs leading to dose modification (interruptions and/or reductions)
- All SAEs
- All SAEs causally related to study treatment
- AEs leading to discontinuation of treatment
- AEs leading to discontinuation of treatment, causally related to treatment
- OAEs
- OAEs causally related to treatment

In addition, a truncated AE table of most common AEs, showing all events that occur in at least 5% of patients overall will be summarised by PT, by decreasing frequency. This cut-off may be modified after review of the data.

AEs will be assigned CTCAE grades and summaries of the number and percentage of patients will be provided by maximum reported CTCAE grade, SOC, PT and actual treatment group. Fluctuations observed in CTCAE grades during the study will be listed (where collected).

AEs with outcome of death, SAEs, AEs leading to discontinuation of treatment, AEs causally related to treatment and OAEs will be listed.

Any AE occurring before study treatment will be included in the data listings but will not be included in the summary tables of AEs.

A separate summary of AEs occurring more than 28 days after discontinuation of AZD9291 (where reported) as well as those occurring prior to treatment will be produced. These events will not be included in other AE summaries.

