To assess any changes in EGFR mutation status (including T790M) using the mandated serial plasma samples coupled with a high sensitivity method yet to be determined (retrospective)	Assessment of EGFR mutation status in serial plasma samples
To explore the relationship between PK and selected endpoints (which may include efficacy, safety, and/or PRO), where deemed appropriate.	Correlation of PK with other primary/secondary/exploratory endpoints in patients treated with AZD9291.

Target patient population

Male and female patients aged 18 years and over (patients from Japan/Taiwan aged at least 20 years) with histologically confirmed diagnosis of primary non-squamous non-small cell carcinoma of the lung, with complete surgical resection of the primary tumour, and who were classified post-operatively as Stage IB, II or IIIA on the basis of pathologic criteria are eligible for this study. Recruitment of patients with stage IB disease will be closed when approximately 210 (30%) have been randomised and recruitment of patients with stage II-IIIA disease will be closed when approximately 490 (70%) have been randomised. Patients must be confirmed to have a tumour that harbours one of the most common EGFR mutations known to be associated with EGFR-TKI sensitivity (Ex19Del; L858R) either alone or in combination with other EGFR mutations as confirmed by a central test.

Patients may have received prior adjuvant platinum doublet chemotherapy for a maximum of 4 cycles in accordance with standard of care but must not have received prior radiotherapy. Pre-operative (neo-adjuvant) platinum based or other chemotherapy is not allowed.

Duration of treatment

Treatment with AZD9291 (80 mg once daily) or placebo will commence following randomisation. Patients will continue on randomised treatment until recurrence of disease, treatment discontinuation criterion is met or treatment is completed. The maximum treatment duration period is 3 years (156 weeks). Should there be any patients on study drug at the time of data cut –off for primary analysis, they may continue treatment until 3 years (156 weeks) treatment is completed or a discontinuation criterion is met.

For patients eligible for open-label osimertinib upon recurrence:

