1.4 Unplanned Interim Analysis of ADAURA (IDMC7)

Following the recommendation of the IDMC after their 7th meeting, an interim analysis was conducted with a DCO of 17 January 2020 ([Wu et al 2020](#)).

A total of 682 patients were randomised to receive treatment with osimertinib 80 mg once daily (N=339) or placebo (N=343). Demographic and disease characteristics of randomised patients were well-balanced between the treatment arms.

The HR for DFS in patients with stage II-IIIA disease was 0.17 (99.06% CI: 0.11, 0.26), demonstrating a statistically significant and clinically meaningful 83% reduction in the risk of disease recurrence or death for patients treated with osimertinib compared with patients treated with placebo.

The HR for the overall population was 0.20 (99.12% CI: 0.14, 0.30), demonstrating a statistically significant and clinically meaningful 80% reduction in the risk of disease recurrence or death for patients treated with osimertinib compared with patients treated with placebo.

At the time of the DCO, OS data were immature with 29 events overall (4.3% of patients): 9 in the osimertinib arm and 20 in the placebo arm.

IDMC considered this data to be indicative of overwhelming efficacy in the osimertinib arm in terms of primary endpoint. The safety profile of patients treated with osimertinib in ADAURA was considered consistent with previous trials with osimertinib. Based on the totality of the data from ADAURA, FLAURA and the approved label for osimertinib, access to open-label osimertinib for eligible patients in the ADAURA study was introduced (see Section 3.3). Patients and investigators remain blinded to individual treatment allocations. Following disease recurrence, at the request of the Investigator patients may be unblinded to aid future treatment decisions (see Section 3.8).

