Following complete resection and prior to treatment initiation, all patients will be required to have a baseline computer tomography (CT) scan (chest and abdomen including liver and adrenal glands) within 28 days of study treatment initiation to confirm that disease is not present. Patients will continue on randomised treatment until recurrence of disease, treatment discontinuation criterion is met, or treatment is completed. The treatment duration period is three years. Patients being on study treatment at the time of DFS primary analysis may continue treatment until discontinuation criterion is met or three years treatment is completed. The study database will be locked at this point. A further analysis will be performed if there are significantly less than 70 DFS events in the IB population at the time of the primary analysis. If more mature data on Overall Survival is required, then it may be analysed at a later timepoint. Once the study is closed serious adverse events (SAEs) will only be reported as per Section 6.4 of the protocol.

Patients will undergo safety assessments at baseline, two weeks, four weeks, 12 weeks and every 12 weeks until treatment is completed or discontinued. All study patients must have a 28 day follow up visit after treatment is stopped.

Patients will undergo regular radiological assessments for disease recurrence at 12 weeks, 24 weeks and then every 24 weeks until five years, then yearly thereafter. DFS shall be measured from the day of randomisation until date of recurrence or death (by any cause) in the absence of recurrence by investigational site assessment.

Patients who discontinue treatment prior to disease recurrence will continue to be followed for DFS according to study plan. Following disease recurrence, patients will undergo radiological imaging for subsequent progression in accordance with local clinical practice and will be

[figure not shown]
followed for survival every six months until five years post randomisation, then yearly thereafter. Follow up will continue until the study is closed.

At disease recurrence, patients will be restaged according to the 7th edition of AJCC Cancer Staging Manual, 2010, and all sites of NSCLC relapse will be recorded. Treatments received by the patient after relapse will be determined by the physician. Post recurrence cancer treatments and procedures will be recorded.

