2.1.2. Safety Analysis Set

The safety analysis set will consist of all patients who received at least one dose of study treatment.

Safety data will not be formally analysed but summarised using the safety analysis set, according to the treatment received; i.e. erroneously treated patients (e.g. those randomised to treatment A but actually given treatment B) will be summarised according to the treatment they actually received. If a patient received both treatments, then they will be summarised according to the active treatment.

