4.3.8.4. Exposure

Exposure will be summarised for safety analysis set. The following summaries will be produced:

- Summary of duration of exposure of study treatment including total exposure, actual exposure, and cumulative exposure over time (number and percentage for: ≥ 1 day, ≥ 6 months, ≥ 12 months, ≥ 18 months, ≥ 24 months, ≥ 30 months, ≥ 36 months)
- Summary of interruptions and reductions of study treatment

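### General adverse event tables give only crude percentages although time at risk ends with dosing at recurrence; add period-specific exposure-adjusted rates beside them

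*SAP*

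**What the plan says.** SAP 4.3.8.1 states that all AEs "will be summarised descriptively by count (n) and percentage (%) for each treatment arm". It then lists tables by system organ class and preferred term, all as number and percent of patients. They include all AEs, grade 3 or higher AEs, SAEs and AEs leading to discontinuation. Patients are counted once per term: "multiple events per patient will not be accounted for apart from on the episode level summaries".

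For the primary and later analyses, the summary window after dosing is defined as "28 days following discontinuation of study treatment and before starting subsequent cancer therapy". SAP 1.2 sets when dosing ends: "Patients will continue on randomised treatment until recurrence of disease, treatment discontinuation criterion is met, or treatment is completed". The protocol synopsis gives the cap: "The maximum treatment duration period is 3 years (156 weeks").

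Protocol 1.4 reports the interim result: "The HR for the overall population was 0.20 (99.12% CI: 0.14, 0.30"). The stage II-IIIA hazard ratio was 0.17.

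The SAP also plans some summaries that take account of time:
- SAP 4.3.8.4 plans a "Summary of duration of exposure of study treatment including total exposure, actual exposure, and cumulative exposure over time".
- SAP 4.3.8.2 plans time to first onset, time to first grade 3 or higher event, and duration for AEs of special interest (AESIs). It also plans life tables and prevalence plots for rash, diarrhoea, fatigue and stomatitis.
- SAP 3.3.5 derives Total Safety Follow-up for each patient, but no table is said to use it as a denominator.

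SAP 2.1.2 keeps safety descriptive: "Safety data will not be formally analysed but summarised using the safety analysis set".

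**The concern.** Recurrence ends dosing, and the end of dosing closes the AE window soon after. The time during which a patient can contribute an AE to the tables therefore depends on the primary outcome. If recurrence is much more frequent on placebo, recurrence-driven truncation falls mainly on that arm. A percentage of patients ever affected does not show how long each arm was observed.

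The safety objective is the profile of AZD9291 compared with placebo. Readers will make that comparison from the side-by-side percentages, whether or not a test is attached. For events that build up over three years, part of any difference may be observation time alone, and the general tables give no means of judging how much. This matters in patients with completely resected disease, in whom the tolerability of long treatment weighs heavily in benefit-risk.

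**Working it through.** **The plan's own figures.** The documents give no AE or exposure figure by arm to reproduce. The DFS assumptions behind the model do reproduce. Medians are 40/0.70 = 57.1 and 46/0.70 = 65.7 months (stated: 57 and 66). The critical hazard ratio at 247 events is exp(-1.96 × 2/√247) = 0.779 (stated: 0.78).

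**Inputs.**
- Cap on treatment: 156 weeks, T = 156 × 7/30.4375 = 35.9 months.
- Placebo median DFS, overall: 46 months, exponential (SAP 1.3). Hazard l0 = ln 2/46 = 0.01507 per month.
- Osimertinib hazard: 0.20 × l0 = 0.003014 (Protocol 1.4), or 0.70 × l0 = 0.01055 (design).
- Assumed: DFS events and the cap are the only reasons to stop, and all patients could reach the cap. The 28-day tail is ignored; it adds at most about one month in each arm.

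**Mean time on treatment** = (1 - exp(-l × T))/l.
- Placebo: (1 - 0.582)/0.01507 = 27.7 months.
- Osimertinib at 0.20: (1 - 0.897)/0.003014 = 34.0 months, ratio 1.23.
- Osimertinib at 0.70: (1 - 0.685)/0.01055 = 29.9 months, ratio 1.08.

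**Crude percentage for an event with the same constant hazard a in both arms** = a/(a + l) × (1 - exp(-(a + l) × T)), with a = 0.005 per month (assumed).
- Placebo: 12.8%.
- Osimertinib at 0.20: 15.6%, relative excess 22%.
- Osimertinib at 0.70: 13.8%, relative excess 7 to 8%.
- Stage II-IIIA inputs (median 40 months, hazard ratio 0.17): 12.3% against 15.6%.

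**Calibration to the January 2020 cut-off.** I fitted the model to 196 events in 682 patients at hazard ratio 0.20. Uniform entry was assumed, with shortest follow-up 6 to 12 months and longest 50 to 53 months. Mean exposure is 19.4-21.6 months on placebo and 24.8-27.1 on osimertinib (ratio 1.26-1.28). An equal hazard of 0.10 per year would read 14.6-16.1% against 18.3-20.0%.

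**Early-onset events.** Take a 10% risk confined to months 0 to 3 in both arms, a hazard of -ln(0.9)/3 = 0.0351 per month, with DFS hazard ratio 0.20. The crude figures are 9.8% and 10.0%, so the percentage is almost unaffected.

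**The same early event under one overall rate.** Mean time to first event or end of treatment is 25.1 months on placebo and 30.8 on osimertinib. The rates are 0.0978/25.1 × 1200 = 4.68 and 0.0996/30.8 × 1200 = 3.88 per 100 patient-years, a ratio of 0.83 with no true difference. Restricted to months 0 to 3, both arms give 42.1 per 100 patient-years, a ratio of 1.00. This is why the rate has to be split by period.

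**Other discontinuation.** Exposure is equal when osimertinib carries an excess non-recurrence stopping hazard of l0 × (1 - HR). Over the treatment period this is 1 - exp(-l0 × 0.80 × T) = 35% at hazard ratio 0.20, and 1 - exp(-l0 × 0.30 × T) = 15% at 0.70. If such stopping were 3% on placebo and 20% on osimertinib over 36 months (assumed), the exposure ratio at 0.20 would be 1.12 instead of 1.23.

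**The case against.** The strongest objections, and what remains of each:

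- **No exposure by arm is reported.** A reader might infer that placebo exposure is systematically shorter and that osimertinib must look more toxic than it is. The documents do not support that as fact. Protocol 3.10 lists other reasons to stop, among them adverse events, patient decision and non-compliance. An excess of these on osimertinib would narrow the gap and, if large enough, reverse it. This stands. It does not rescue the crude percentage, which could not reveal a reversal either.
- **The effect depends on event timing.** Early events barely move. This stands, and it limits the point to events that accrue over time.
- **The SAP already has time-aware summaries.** A reader might infer that longer observation and a real rate difference cannot be separated at all. That is too strong: onset, duration and the four life tables help for AESIs, and the exposure tables show whether the arms differ. None of these adjusts the general AE, grade 3 or higher, SAE or discontinuation tables.
- **Safety is descriptive only.** True, so no test should be added. Descriptive tables can still carry a person-time denominator.
- **A rate has its own bias.** This stands. An undivided rate favours the longer-exposed arm for early-onset events, by about 17% in the example above.

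**Conclusion.** The concern holds in a limited form. The general AE tables are crude percentages only, over a window whose length depends on recurrence. Given the reported hazard ratios, placebo time at risk is probably shorter. For steadily accruing events with no drug effect, the relative inflation on osimertinib is about 20% at hazard ratio 0.20 and 7 to 8% at the design value. It is close to nil for early events. An imbalance was foreseeable at planning, since it arises at 0.70 as well.

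These sizes rest on exponential DFS, the planning median of 46 months, a constant event hazard and no stopping other than DFS events and the cap. Other stopping could shrink or reverse them. No efficacy conclusion, alpha allocation or decision rule is touched. The gap is one of presentation in the safety report and is cheap to close.

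**What to change.** Keep the crude percentages. Beside them add descriptive exposure-adjusted first-event rates per 100 patient-years by arm for all AEs, grade 3 or higher AEs, SAEs and AEs leading to discontinuation, with grouped AESIs for consistency. Build time at risk from Total Safety Follow-up in SAP 3.3.5, cut at the first event and at the start of subsequent cancer therapy so that it matches the window in SAP 4.3.8.1. Present the rates by period, for example 0-3, 3-12 and 12-36 months, and state that they are to be read with the percentages. No formal test is needed.

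The cost is a few extra tables from data already collected. The named downside is that a single overall rate would understate early-onset events on the longer-exposed arm (ratio about 0.83 with equal early risk), so an undivided rate should not be shown alone.

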1.3. Number of Patients

Approximately 700 patients will be randomised globally in a 1:1 ratio (AZD9291: placebo) to this study. The primary endpoint of the study is DFS based on investigator assessment. DFS will first be tested in the subset of patients with Stage IIA-III A cancer. If statistical significance is shown for DFS in the subset of patients with Stage IIA-III A cancer, then it will be tested for the overall population with the test mass split between first and second analyses.

The primary analysis of DFS will occur when approximately 247 disease recurrence events have been observed in approximately 490 patients who are in Stage IIA-III A (i.e. non-IB). If the true DFS hazard ratio (HR) for the comparison of AZD9291 versus placebo in this patient population is 0.70, 247 disease recurrence events will provide 80% power to demonstrate a statistically significant difference in DFS at a 5% two-sided significance level (translating to an improvement in median DFS from 40 months to 57 months, assuming DFS is exponentially distributed). The minimum DFS HR that would be statistically significant (i.e. $p < 0.05$, two-sided) is 0.78.

If the true DFS HR for the comparison of AZD9291 versus placebo in the overall population is 0.70, 314 disease recurrence events will provide approximately 90% power to demonstrate a statistically significant difference in DFS at a 4% two-sided significance level (translating to an improvement in median DFS from 46 months to 66 months, assuming DFS is exponentially distributed). The minimum DFS HR that would be statistically significant (i.e. $p < 0.04$, two-sided) is 0.79.

At the time of the primary analysis it is anticipated that approximately 195 OS events (28% maturity) will have occurred (assuming a median OS of 96 months for the placebo arm) in the overall population. If the true OS HR for the comparison of AZD9291 versus placebo is 0.66, 195 death events provide approximately 80% power to demonstrate a statistically significant difference at the 4% (two-sided) significance level. With 195 death events and assuming a true OS HR of 0.85 there is approximately 90% chance of observing an HR < 1.02 .

Assuming 28 months non-linear recruitment the data cut-off for the primary analysis is estimated to occur approximately 68-70 months after first patient randomised.

It is estimated that 3200 patients will be screened in order to randomise 700 patients.

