Table 2 Important Protocol Deviations

Criteria Type	Important Deviation Description
	
 • Pre-operative or post-operative or planned radiation therapy for the current lung cancer. • Any other prior anticancer therapy, including investigational therapy, for treatment of NSCLC other than standard platinum based doublet post-operative adjuvant chemotherapy. • Treatment with an investigational drug within five half-lives of the compound or any of its related material, if known. • Past medical history of ILD, drug-induced ILD, radiation pneumonitis which required steroid treatment, or any evidence of clinically active ILD.
IP Administration/ Study Treatment	
 • Patient was randomized but did not receive any treatment • Patient received medication in error e.g. patient dosed but not fully eligible for study treatment or patient received the incorrect treatment e.g. did not receive the treatment they were randomised to. • Patients with corneal ulceration and/or ILD who resume study treatment.
Procedures/Tests	
 • Baseline disease assessment performed more than 28 days prior randomization i.e. not performed during screening window. • Disease Recurrence scans not performed in accordance with the protocol time schedule RELATIVE to RANDOMISATION date or not at all.
Disallowed Medications	
 • Patient receiving anti-cancer therapies (e.g. anticancer drugs, radiotherapy) or other concomitant strong CYP3A inducers or herbal medications which are strong CYP3A inducers during the study, other than IP.

The following summary will be provided:

- A summary of the number and percentage of patients with an important protocol deviation by treatment group and overall and by type of deviation (Analysis set: FAS)

A by-patient listing of important protocol deviations will be provided in the CSR.

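### The truncated common-AE table sets its 5% cut on both arms pooled, so it can omit a term seen in up to about 10% of osimertinib patients, although the full by-arm tables still show it

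*SAP*

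**What the plan says.** SAP 4.3.8.1 adds a truncated table of the most common AEs, "showing all events that occur in at least 5% of patients overall will be summarised by PT, by decreasing frequency". It then says: "This cut-off may be modified after review of the data". It gives no per-arm or either-arm criterion, and no rule for when or in which direction the cut-off may move.

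The truncated table comes on top of fuller displays in the same section. All AEs "will be summarised descriptively by count (n) and percentage (%) for each treatment arm". The SAP also states: "Summary information (the number and percent of patients by treatment) by SOC and PT will be tabulated for". The list that follows covers all AEs, causally related AEs, grade 3 or higher, fatal AEs, SAEs, AEs leading to dose modification or discontinuation, and others. None of these carries a frequency cut. All reported AEs are listed as well.

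The population is set in SAP 4.3.8: "The safety analysis set will be used for all safety and tolerability tables, figures and listings except where expressly noted". Allocation is 1:1 (SAP 1.3).

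**The concern.** In a 1:1 placebo-controlled trial, a cut on the pooled rate is roughly a cut on the average of the two arm rates. A term confined to the active arm must therefore reach about twice the nominal 5% before it qualifies. A background term with the same rate in both arms qualifies at 5%.

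The table's purpose is to show which events are common. A reader who takes it as the list of events affecting at least 5% of osimertinib patients would be misled, because terms between 5% and about 10% on osimertinib can be absent when they are rare on placebo. Safety and tolerability against placebo is a stated objective, and the patients are disease-free after resection and treated for up to three years. A moderately frequent drug-related event is something such a summary should display.

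**Working it through.** The plan derives no figure from the 5% cut, so there is none to reproduce. The check is direct counting.

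**What overall means.** SAP 2.2 sets the word beside the arms: "A summary of the number and percentage of patients with an important protocol deviation by treatment group and overall and by type of deviation". There it plainly means both arms together. SAP 4.3.8.2 uses the word once in contrast to maximum CTCAE grade, so it can also mean any grade. In 4.3.8.1, however, it qualifies patients in a percentage threshold, where any-grade does not fit. Pooled is the natural reading.

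**Inputs.** From Protocol 1.4: "A total of 682 patients were randomised to receive treatment with osimertinib 80 mg once daily (N=339) or placebo (N=343". The number treated is not in the documents, so the randomised numbers are used as an assumption and varied below.

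**Rule.** A term is shown if x_active + x_placebo ≥ ceil(0.05 × N_total).

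- 0.05 × 682 = 34.1, so 35 patients are needed and 34 is the largest omitted total.
- With x_placebo = 0, the largest omitted osimertinib rate is 34/339 = 10.0%. The pooled rate is 34/682 = 4.99%.

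**Non-zero placebo rates (339/343).**

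| Placebo rate | Placebo patients | Largest omitted osimertinib count | Rate |
|---|---|---|---|
| 0% | 0 | 34 | 10.0% |
| about 1% | 3 | 31 | 9.1% |
| about 2% | 7 | 27 | 8.0% |
| about 3% | 10 | 24 | 7.1% |

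**Contrast.** A term in 18/339 (5.3%) and 18/343 (5.2%) totals 36 and is kept. A term in 24/339 (7.1%) and 9/343 (2.6%) totals 33 and is dropped.

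**Other denominators, zero on placebo.**

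- Planned 350 per arm: 0.05 × 700 = 35, so 34/350 = 9.7% is omitted.
- Two untreated osimertinib patients (337/343): 33/337 = 9.8%.
- Nine untreated osimertinib patients (330/343): 33/330 = 10.0%.
- Nine untreated placebo patients (339/334): 33/339 = 9.7%.

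The ceiling stays between 9.7% and 10.0%.

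**Under an either-group rule.** 0.05 × 339 = 16.95, so a term seen only on osimertinib appears from 17/339 (5.0%) instead of 35/339 (10.3%). No row is lost: the pooled rate is a weighted average of the two arm rates, so any term at 5% or more pooled is at 5% or more in at least one arm.

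**The case against.** The strongest reply is that the SAP already reports these events. The truncated table supplements untruncated by-arm tables, and AEs of special interest have their own summaries in 4.3.8.2 with no 5% cut. SAP 2.1.2 says safety data are summarised and not formally analysed. No test, estimate or safety decision rests on which rows appear. This stands, and it confines the point to presentation.

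A reader might go further and infer that a pooled cut selects against exactly the events that differ between arms, so that the drug looks more like placebo than it is. The documents do not support that. The cut depends only on the total count. It keeps 35/339 against 0, it drops a term just under 5% in both arms, and it drops a placebo-only excess as readily as an osimertinib-only one. Summaries are by treatment group unless otherwise specified (SAP 4.2), so each retained row still shows its difference.

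It can also be said that no named term is shown to be affected. The protocol's phase I all-grade rates at 80 mg are 33% for diarrhoea and 32% for rash (Protocol 1.1). Even with none on placebo these pool to 33% × 339/682 = 16.4% and 15.9%, so both would appear. ILD at 3.9% (Protocol 1.5) falls below 5% under either rule. This is fair: the gap concerns mid-frequency terms that the documents do not identify.

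Finally, the cut-off may be modified, so it could be lowered and omitted rows restored. Omission is therefore the default, not a certainty. But no criterion is given, and the possibility of later repair is no reason to leave the default as it is.

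**Conclusion.** The point holds as a minor presentation matter. As written, the common-AE table can omit a term in up to 34/339 (10.0%) of osimertinib patients when no placebo patient has it. The limit falls to about 9.1%, 8.0% or 7.1% with placebo at about 1%, 2% or 3%. A term at about 5.2% in both arms is kept.

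This rests on the pooled reading of overall and on randomised numbers standing in for the safety set. The alternative denominators tried move the ceiling only between 9.7% and 10.0%.

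A reader might infer that such events would go unreported. They would not: they appear by arm in the untruncated SOC/PT tables and in the listings. Type I error and the efficacy conclusions are untouched. Only the common-AE summary is incomplete for the active arm.

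**What to change.** In SAP 4.3.8.1, change the criterion to *at least 5% of patients in either treatment group*. SAP 3.1.2 already uses an either-group rule, with a minimum of 10 patients, to decide which visits are summarised, so the wording would be consistent within the plan.

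The cost is a few words and a slightly longer table. Because the rule selects on the higher arm, it will also admit a few more chance imbalances. This SAP edition (23 June 2020) already follows the IDMC's April 2020 recommendation to unblind, so a change made now should be recorded as a post-unblinding change to a display rule. It could still apply to later safety outputs, which Protocol 8.7 and SAP 7 allow for.

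Two further points are optional. The rows could be sorted by frequency in the osimertinib arm, which is a layout choice. The clause allowing the cut-off to be modified could be removed or given a stated criterion. Neither is needed to close the gap.
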